Statistical Analysis Plan

Document Control

Title: Statistical Analysis Plan for the Study of SGLT2 Inhibitors in Lupus Nephritis Patients

Protocol ID: [NCT05748925] Version: 1.0 Date: [11/3/2024] Principal Investigator: [[name]] Statistician: [[name]] Approval Signatures: Principal Investigator: [name] Statistician: [name]

Table of Contents

- 1. Introduction
- 2. Study Design
- 3. Study Objectives
- 4. Endpoints
- 5. Sample Size Justification
- 6. Statistical Methods
- 7. Handling of Missing Data
- 8. Interim Analysis
- 9. Safety Analysis
- 10. Data Quality and Management
- 11. Software
- 12. Appendices

1. Introduction

• **Purpose of the SAP**: This document outlines the statistical approach for analyzing data from the clinical trial studying the effects of SGLT2 inhibitors on renal, cardiovascular, and hematological outcomes in lupus nephritis patients.

2. Study Design

Design: Randomized, double-blind, placebo-controlled clinical trial.

Study Duration: Conducted from September 2022 to November 2023

Randomization: Patients were randomly assigned to either dapagliflozin (10 mg once daily) or placebo groups using computer-generated random tables in a 1:1 ratio stratified by age and gender.

Blinding: The study was double-blinded, and all trial staff and participants remained unaware of individual treatment assignments until study completion.

3. Study Objectives

Primary Objective: To evaluate the impact of SGLT2 inhibitors on renal, cardiovascular, and hematological parameters in lupus nephritis patients.

Secondary Objective: To explore changes in body weight, BMI, and other echocardiographic and iron profile parameters over 12 months.

4. Endpoints

Primary Endpoints

Renal Function: Serum creatinine, eGFR, and 24-hour urine protein

Cardiovascular Health: BNP levels and coronary calcification via NCCT

Hematological Parameters: Hemoglobin and erythropoietin levels

Hepcidin Level: Measured before and after intervention

Secondary Endpoints

Body Weight and BMI: Assessed at baseline and follow-up visits.

Echocardiographic Findings: Assessed pre- and post-intervention.

Iron Profile: Serum ferritin and TSAT

5. Sample Size Justification

Calculation: A sample size of 100 patients was targeted, accounting for potential dropouts, to provide sufficient power (80%) at a significance level of 0.05 to detect differences between the two groups.

6. Statistical Methods

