BNP: Brain natriuretic peptide; EF: Ejection fraction; LAD: Left atrial dimension; ESV: End-systolic volume; EDV: End diastolic volume; (Student T test or Mann-Whitney) for continuous data, and chi-square test for categorical data. Continuous data are expressed as mean (SD) or median (minimum – maximum). Categorical data are expressed as number (percentage).; Level of significance < 0.05.

Table (6): Comparison between study and control groups as regard effect of intervention on
 disease activity and renal affection at different time points

	Grouping	Baseline	3 months	6 months	9 months	12 months	P value*
Consumed C3 & C4	Control	5 (12.2%)	5 (12.2%)	4 (9.8%)	6 (14.6%)	10 (24.4%)	0.1
No. (%)	Study	2 (5.3%)	5 (13.2%)	2 (5.3%)	6 (15.8%)	6 (15.8%)	0.1
	P value**	0.4	0.9	0.3	1	0.4	
S. creatinine (mg/dL)	Control	0.8 (0.4, 2.7)	0.9 (0.4, 3.1)	0.9 (0.3- 3.1)	0.9 (0.6, 4)	0.9 (0.6, 5)	0.1
Median (min, max)	Study	0.8 (0.4, 2.6)	0.9 (0.6, 2.6)	0.9 (0.5, 3.1)	1 (0.5, 4.2) a	0.9 (0.5, 5)	0.01
	P value**	0.8	0.8	1	0.5	0.8	
eGFR (ml/min/m²) Mean ± SD	Control	114±51	104±45 a	107±53.8	99±47 a	100.3±44.5 a	0.003
	Study	128±59.7	115±47 A	118±50 A	109±44.5 a, c	115.7±48 a	0.001
	P value**	0.6	0.9	0.8	0.2	0.9	
	Control	0.4(0.06- 3.6)	0.6 (0.03-5)	0.6 (0.03- 7)	0.6 (0.02, 5)	0.5 (0.02 , 8)	0.06
24- hour urinary protein (g/24 hours) Median (min, max)	Study	0.6 (0.07-3)	0.7 (0.01-4)	0.8 (0.02, 4.8)	0.6 (0.05, 4.7)	0.5 (0.02 , 4)	0.07
	P value**	0.3	0.9	0.8	0.6	0.6	
Albumin (g/dL)	Control	3.7±0.4	3.7±0.4	3.6±0.4	3.8±0.4 c	3.9±0.3 a, b, c	0.001
iviean ± SD.	Study	3.7±0.3	3.7±0.5	3.7±0.3	3.8±0.3 c	3.9±0.8 a, c	0.04
	P value**	0.4	0.9	0.1	0.7	0.8	

(*) Within group analysis (repeated measure ANOVA).

(**) Between group analysis (Student T test or Mann-Whitney) for continuous data, and chi-square test for categorical data. Post-hoc analysis;

(a) significance against baseline <0.05; (b) significance against 3 months level <0.05, (c) significance against 6 months level <0.05, (d)

significance against 9 months level <0.05. Continuous data are expressed as mean (SD) or median (minimum – maximum). Categorical data are expressed as number (percentage).

Table (7): effect of intervention on hematological findings between both groups at different time points:

	Grouping	Baseline	3 months	6 months	9 months	12 months	P value*
Haemoglobin (g/dL) Mean ± SD	Control	11.9±1.9	12.2±1.9	11.8±2.5	12±1.9	12.2±1.9	0.08
	Study	11.8±1.8	12.3±1.7	12±2.5	11.9±2.2	12±2	0.06

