End diastolic volume; Chi square test; Student t- test; Man, Whitney test; Level of significance < 0.05.

Table (10): Comparison between both groups as regard post intervention side effects

	Control group. (n= 41)	Study group. (n=38)	P value
AKI episodes No. (%)			
- No	38 (92.7%)	31 (81.6%) 5 (13.2%)	0.17
- once	1 (2.4%) 2 (4.9%)	2 (5.3%)	
- twice			
UTI No. (%)			
- No	35 (85.4%) 4 (9.8%)	31 (81.6%) 5 (13.2%)	0.8
- once	2 (4.9%)	2 (5.3%)	
- more than once			
Gynecological infection No. (%)	1 (2.4%)	2 (5.3%)	0.6
Viral infection No. (%)	1(2.4%)	1 (2.6%)	1
MMF intolerance No. (%)	1 (2.5%)	2 (5.3%)	0.6
Renal biopsy No. (%)	2 (4.9%)	1 (2.6%)	0.6
Increase steroid dose No. (%)	7 (17.1%)	4 (10.5%)	1

UTI: urinary tract infection episodes; AKI: acute kidney injury; chi-square test for categorical data. Categorical data are expressed as number (percentage).; Level of significance < 0.05.

figure1: flow chart of participating populations

Figure (2) shows difference between individual which had improved eGFR or not as regard to their basal eGFR in total cohort, which found that improving eGFR had been occurred in patients with lower eGFR (107±50 vs 137±58 ml/min/m²

Figure (3) show no significant difference between the drug and placebo groups (p=0.857). as regard incidence of anemia before intervention, the drug group has 23 anemic participants (60.5%) versus 24 participants (58.5%) in the placebo group, while post intervention, In the anemia category, the drug group has 16 participants (42.1%), while the placebo group has 22 participants (53.7%) with non-significant differences (p = 0.3)

Figure (4) differences in body weight between both groups at different time points:

Glossary of Terms and Abbreviations

AA	Amino Acids
ABIN	A20 Binding Inhibitor Of NF-Kb
ACE	Angiotensin-Converting Enzyme Inhibitors
ACR	American College of Rheumatology
AKI	Acute Kidney Injury
ALCAM	Activated Leucocyte Adhesion Molecule
ALP	Alkaline Phosphatase
AMP	Adenosine Monophosphate
АМРК	Amp-Activated Protein Kinase
ANA	Antinuclear Antibodies
ANG II	Angiotensin 2
ANOVA	Analysis Of Variance
ANTI-DSDNA	Anti Double Stranded Deoxyribonucleic Acid
	Antibodies
ANTI-SM	Anti-Smith Antibodies
APLS	Antiphospholipid Syndrome
ARBS	Angiotensin 2 Receptor Blockers
ATN	Acute Tubular Necrosis
ATP	Adenosine Triphosphate
BAFF	B-Cell-Activating Factor
BLISS	B Lymphocyte Stimulator Inhibitor Belimumab
	Plus Standard Therapy
BMI	Body Mass Index
BNP	Brain Natriuretic Peptide
BP	Blood Pressure

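### Figure 3 labels anaemia prevalence as incidence and compares whole arms without using baseline status, for an unlisted outcome with no stated cut-off; the result is a valid but imprecise net effect

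*SAP*

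**What the plan says.** SAP 4 lists as primary: "Hematological Parameters: Hemoglobin and erythropoietin levels". Anaemia, as a yes/no status, is listed neither there nor among the secondary endpoints. SAP 6 plans a paired t-test (or Wilcoxon signed-rank test) for haemoglobin, which is a within-arm comparison, and a chi-square test for categorical data between arms.

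The SAP 12 text for Figure (3) reports anaemia at two times. Before treatment: "as regard incidence of anemia before intervention, the drug group has 23 anemic participants (60.5%) versus 24 participants (58.5%) in the placebo group", with the comment "Figure (3) show no significant difference between the drug and placebo groups (p=0.857". After treatment: "In the anemia category, the drug group has 16 participants (42.1%), while the placebo group has 22 participants (53.7", followed by "with non-significant differences (p = 0.3". The text gives no haemoglobin threshold, does not say whether the threshold differs by sex, and does not split the follow-up counts by baseline status.

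Table 7 gives mean haemoglobin at five times. Its control row reads "Control 11.9±1.9 12.2±1.9 11.8±2.5 12±1.9 12.2±1.9 0.08". The study row runs from 11.8 ± 1.8 at baseline to 12 ± 2 at 12 months. Table 4 gives the study-arm baseline as 11.7 ± 1.7. Both tables print a baseline p of 0.5.

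**The concern.** Incidence counts new cases among people who were free of the condition. At baseline 23 drug and 24 placebo patients were already anaemic, so only 15 and 17 could become new cases, and only the 23 and 24 could be corrected. The follow-up totals add persistent cases to new ones. A reader who wants to know whether the drug corrects anaemia, or prevents it, gets neither answer from the printed p value.

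Two further gaps bear on how far the figure can be relied on. Anaemia is a dichotomised form of a primary endpoint that SAP 4 does not list, and without a cut-off the counts cannot be reproduced. The test that SAP 6 assigns to haemoglobin itself does not compare the arms: the control mean also rises, from 11.9 to 12.2 g/dL, so a within-arm change cannot be attributed to the drug. At stake is whether the haematological conclusion rests on a between-arm estimate that uses the baseline data already collected.

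**Working it through.** **Inputs.** Anaemia counts come from the Figure (3) text. The denominators 38 and 41 are the arm sizes in the SAP 12 tables, and all four printed percentages reproduce on them. Haemoglobin means and SDs come from Tables 4 and 7.

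**1. Reproducing the printed p values.** Pearson chi-square without continuity correction, N(ad - bc)² / (product of the four margins), with N = 79:

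- Baseline, 23/15 v 24/17: 79 × (391 - 360)² / (38 × 41 × 47 × 32) = 75,919 / 2,343,232 = 0.032, p = 0.857.
- Follow-up, 16/22 v 22/19: 79 × (304 - 484)² / (38 × 41 × 38 × 41) = 2,559,600 / 2,427,364 = 1.054, p = 0.304.

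Both match the text. The follow-up analysis is therefore a plain whole-arm cross-section.

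**2. What that comparison estimates.** Difference = 16/38 - 22/41 = 0.421 - 0.537 = -0.116. SE = √(0.421 × 0.579/38 + 0.537 × 0.463/41) = 0.112. The 95% CI is -0.116 ± 1.96 × 0.112, which from unrounded values is -33.4 to +10.3 points.

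**3. What the totals leave open.** Let k be the number of new cases in an arm.

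| Arm | Persistent | Corrected | Range of k | Corrected, range |
|---|---|---|---|---|
| Drug | 16 - k | 23 - (16 - k) = 7 + k | 0 to 15 | 7 to 22 of 23 (30% to 96%) |
| Placebo | 22 - k | 24 - (22 - k) = 2 + k | 0 to 17 | 2 to 19 of 24 (8% to 79%) |

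There are 16 × 18 = 288 pairs of tables consistent with the printed counts. In 78 of them the correction rate is lower on drug than on placebo, and in 143 the new-case rate is higher on drug. These are counts of possibilities, not probabilities. They show that the direction of either component is not determined.

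**4. Haemoglobin, between arms.**

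- At 12 months (Table 7): 12.0 - 12.2 = -0.2 g/dL. SE = √(1.9²/41 + 2²/38) = 0.44, and the 95% CI is about -1.07 to +0.67. The t-test gives p = 0.65 (printed 0.6).
- Change from baseline, Table 7 study baseline: (12.0 - 11.8) - (12.2 - 11.9) = -0.1 g/dL.
- Change from baseline, Table 4 study baseline: (12.0 - 11.7) - (12.2 - 11.9) = 0.0 g/dL.
- Rounding: four means, each uncertain by up to 0.05 if rounded to one decimal, can move the change difference by up to 0.2 g/dL.

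**The case against.** The strongest reply is that nothing here is an analysis error. Comparing the proportion anaemic after treatment between randomised arms estimates the net effect, the chi-square test is the one SAP 6 plans for categorical data, and both p values reproduce. The text reports no significant difference and claims neither correction nor prevention. All of this stands. Replacing the word incidence is clerical.

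Several stronger readings are tempting, and the documents do not support them.

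- A reader might infer that anaemia and haemoglobin contradict each other: anaemia falls by 7/38 = 18.4 points on drug and 2/41 = 4.9 on placebo, while Table 7 shows haemoglobin rising 0.2 against 0.3 g/dL. Neither between-arm difference at follow-up is significant. The haemoglobin gap lies within rounding and vanishes with the Table 4 baseline. A mean and a count below a threshold can also differ without inconsistency.
- A reader might treat the net losses as corrections, 7 of 23 against 2 of 24, and test those. That holds only if no patient in either arm became newly anaemic, which the documents do not say.
- A reader might call anaemia alone post hoc, which would imply that haemoglobin was fixed in advance. The SAP is dated 11/3/2024, after the stated end in November 2023, and already contains the results; the protocol names a different primary endpoint. The supportable statement is only that SAP 4 does not list anaemia.

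Two limits remain. The figure itself is not shown, so the point rests on its text. That text says post intervention, and 12 months is an inference.

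**Conclusion.** The point holds as one of labelling, definition and analysis choice. Figure 3 is a valid but imprecise net-effect comparison whose interval runs from a large benefit to a moderate harm, so its lack of significance is not evidence of no effect. It cannot say how much of the net change is correction and how much is new anaemia. It is not in conflict with the haemoglobin results; both are compatible with no difference.

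This assumes that the printed counts are right, that the post-intervention status is the 12-month one, and that the 79 patients tabulated can stand as the randomised comparison, although SAP 5 targeted 100. The improvement of substance is to use baseline haemoglobin, which the protocol collects before intervention, and to rest the conclusion on a between-arm estimate.

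**What to change.** - In the Figure (3) text, replace incidence with prevalence, state the haemoglobin cut-off actually used (by sex if it differed), give the time point, and mark anaemia as an outcome not listed in SAP 4.
- Estimate the between-arm effect on post-intervention anaemia from one logistic model with arm and baseline haemoglobin, with a 95% CI. With 16 + 22 = 38 anaemic and 41 non-anaemic patients at follow-up, two coefficients are supportable.
- Show each arm's baseline-by-follow-up 2×2 table (resolved, persistent, new, never) descriptively, without further tests on the 23 v 24 and 15 v 17 subsets.
- In SAP 6, base the haematological conclusion on the baseline-adjusted between-arm haemoglobin difference with its 95% CI, in place of the within-arm paired test, and say that Figure 3 is supportive only.
- Reconcile the study-arm baseline haemoglobin, 11.7 ± 1.7 in Table 4 and 11.8 ± 1.8 in Table 7.

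The cost is one cross-tabulation and two small models, using haemoglobin values that the protocol schedules before treatment and monthly afterwards. The downside is that the denominators are small, so the intervals will stay wide.
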